The target sample size is 100 patients for this Phase II study. Allowing for a 15% ineligibility rate, the total sample size is 115 patients. Accrual is anticipated to be completed within 5 years of institutional IRB approval. This Phase II trial will provide information to guide future Phase III studies. Sample size determination is based on the late toxicity endpoint. A single-stage Fleming design will be used to test the null hypothesis that the late unacceptable radiation toxicity probability at 2 years p is < 0.05 versus the alternative hypothesis that toxicity probability at 2 years is > 0.15 . Unacceptable toxicity will be defined as grade 3 or higher toxicity. If 10 or fewer patients experience late radiation toxicities at 2 years, the null hypothesis will not be rejected and then the regimen will be considered for a phase III study. If at least 10 patients experience late radiation toxicities at 2 years, the null hypothesis will be rejected. This design has a power of 89% and a type I error rate of 0.10.

Analysis Plan

1. Number and percentage of subjects for each toxicity will be summarized overall by body system and by onset time (acute: ≤ 90 days of treatment start and late: >90 days of treatment start). The tabulation will also be separated by toxicities of Grade 3 and above.
Future studies incorporating DE-SBRT would be worthwhile if the rate of grade 3 GU/GI toxicity was $\leq 10\%$.
2. Biochemical disease-free survival, disease-free survival, disease-specific and overall survival curves will be calculated and presented by the methods of Kaplan and Meier.
3. The proportion of patients with local and distant failure will be reported with a 95% binomial confidence interval.
4. General health related and disease specific quality of life measurements will be summarized over time. Graphical displays will be created for each patient's trajectory over time and also summarized using the average for all patients.

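### The late-toxicity count can settle the primary test before accrual ends, but the protocol ties no action to the running count

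*Protocol*

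**What the plan says.** All the design statements are in Section 8, Study Design.

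- Size: "The target sample size is 100 patients for this Phase II study". With a 15% allowance for ineligible men, 115 are to be enrolled.
- Accrual: "Accrual is anticipated to be completed within 5 years of institutional IRB approval".
- Test: "A single-stage Fleming design will be used". The null is stated as "the late unacceptable radiation toxicity probability at 2 years p is < 0.05" and the alternative as "toxicity probability at 2 years is > 0.15". An event is toxicity of grade 3 or higher.
- Decision: "If 10 or fewer patients experience late radiation toxicities at 2 years, the null hypothesis will not be rejected", and the regimen is then considered for phase III. The next sentence rejects when the count is 10 or more, so exactly 10 events falls under both decisions.
- Stated error rates: power 89% and type I error 0.10.

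Section 7 schedules toxicity evaluation weekly during treatment, at 1 month, at 6, 12, 18 and 24 months, and yearly after that. Late toxicity starts after 90 days from the start of treatment in Sections 7 and 8, but after six months in the Section 2 objectives. The protocol as shown has no interim look, accrual pause or toxicity boundary, and it does not say when the count is read.

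**The concern.** The decision depends on 10 or 11 events. Late events can be recorded from 3 or 6 months after treatment, while accrual may run for 5 years, so much of the count arrives while men are still being entered. When the rejection number is reached, the test that Section 8 makes primary has failed, whatever happens to later patients. Nothing in the text then asks anyone to stop and look. Men could go on being entered under a safety test whose result is already fixed.

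**Working it through.** **1. The plan's own figures.** With X ~ Binomial(100, p), type I error is P(X ≥ r) at p = 0.05 and power is P(X ≥ r) at p = 0.15.

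| Reject at | Type I error | Power |
|---|---|---|
| r = 11 | 0.0115 | 0.901 |
| r = 10 | 0.0282 | 0.945 |

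The stated power of 89% is close to r = 11. The stated type I error of 0.10 is not reproduced by either cut-off. That is a separate matter, and the point below holds for both.

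**2. Chance that the count is reached during accrual.** Inputs from Section 8: n = 100, r = 10 or 11, accrual A = 5 years at most. Assumed: entry times uniform over A, onset T uniform from 0.25 to 2 years, events known when they occur, no loss to follow-up. A man's event is seen by the end of accrual with probability

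q = p × (1 − E[T]/A) = p × (1 − 1.125/5) = 0.775p,

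and the count at that time is Binomial(100, q). At p = 0.15, q = 0.11625, so P(X ≥ 11) = 0.624 and P(X ≥ 10) = 0.739.

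**3. Men entered after the count is reached.** With G(t) = P(entry time + T ≤ t), the expected number is

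∫₀ᴬ (100/A) × P(Binomial(99, pG(t)) ≥ r) dt.

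This averages over all trials, including those where the count is not reached.

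| True rate | q | Reached, r = 11 | Men after | Reached, r = 10 | Men after |
|---|---|---|---|---|---|
| 5% | 0.039 | 0.002 | 0.01 | 0.005 | 0.05 |
| 10% | 0.078 | 0.152 | 1.7 | 0.247 | 3.2 |
| 15% | 0.116 | 0.624 | 10.6 | 0.739 | 14.8 |
| 20% | 0.155 | 0.922 | 23.3 | 0.958 | 27.9 |
| 25% | 0.194 | 0.991 | 33.6 | 0.996 | 37.5 |

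A simulation of the same model (40,000 runs per setting) agrees. At 15% it gives 62.3% and 10.6 men for r = 11, and 73.9% and 14.8 men for r = 10. Among trials where the count is reached, about 17 or 20 men follow.

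**4. Sensitivity at a true rate of 15%.** The formulas are the same with E[T] and A changed.

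| Accrual, counting of events | q | Reached, r = 11 / 10 | Men after, r = 11 / 10 |
|---|---|---|---|
| 5 years, onset 3–24 months | 0.116 | 0.624 / 0.739 | 10.6 / 14.8 |
| 5 years, onset 6–24 months | 0.113 | 0.578 / 0.700 | 9.2 / 13.0 |
| 4 years, onset 3–24 months | 0.108 | 0.519 / 0.647 | 7.5 / 11.0 |
| 3 years, onset 3–24 months | 0.094 | 0.335 / 0.464 | 3.6 / 5.9 |
| 5 years, counted only at 24 months | 0.090 | 0.288 / 0.412 | 2.9 / 4.8 |
| 3 years, counted only at 24 months | 0.050 | 0.012 / 0.028 | 0.04 / 0.12 |

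In the last row q = 0.15 × (1 − 2/3) = 0.05, and the issue almost disappears.

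**5. Effect on the error rates.** The final count in a fixed set of patients is at least as large as any running count in that set. Running count ≥ r therefore implies final count ≥ r, and a final count ≥ r means the running count reached r at some time. The two rules reject in exactly the same trials, so step 1 is unchanged. This fails if the tally covers a wider set than the test. Counting all 115 against r = 11 gives 0.029 and 0.967 in place of 0.0115 and 0.901.

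**The case against.** A single-stage design is legitimate and by definition has no interim decision. The protocol does not misstate its number of looks, and toxicity is reviewed at regular visits, so events would be seen. All of that stands. That the count is read only at the end is an inference from the words single-stage and from the lack of any running rule. The point is therefore a gap that is cheap to close, not an error in the design.

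The size also depends on assumptions the protocol does not fix. Faster accrual or counting only at 2 years shrinks it, and both together nearly remove it at 15%.

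Three stronger readings are tempting, and the documents do not support them.

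- A reader might say that later men would receive a regimen the trial has already declared unacceptable. Rejection means evidence of a rate above 5%. Section 8 links phase III consideration to non-rejection and gives rejection no consequence for accrual. Its analysis plan also calls future studies worthwhile at a grade 3 GU/GI rate of up to 10%. What has happened at that point is that the primary test has failed.
- A reader might count events in all 115 men and conclude that about 19 men follow the 11th event at 15%. The cut-off belongs to the target of 100, and 115 includes the ineligibility allowance. On 100 men the figure is about 11. Likewise, the chance of ever reaching 11 at a true 5% is 0.029 with 115 men but 0.0115 with 100, and about 0.002 during accrual.
- A reader might assume that any running tally leaves the error rates untouched. Step 5 shows that it must cover the same patients and use the same cut-off.

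**Conclusion.** The point holds as a moderate, inexpensive improvement. The protocol uses a count that can only rise, collects it during an accrual of up to 5 years, and says nothing about what follows when it reaches the rejection number. Under uniform 5-year accrual of 100 evaluable men with onset over 3 to 24 months, the protocol's own alternative of 15% is more likely than not to trigger this before accrual ends, with about 11 or 15 men entered afterwards on average. At 20% it is about 23 or 28, and at 25% about 34 or 38. With only one unfavourable change (3-year accrual, or counting only at 2 years) the average at 15% is about 3 to 6. At a true 5% the trigger occurs during accrual in about 0.5% of trials at most. These figures illustrate the size, because neither the accrual pattern nor the onset distribution is in the protocol.

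**What to change.** First reconcile two conflicts on which any tally depends: which decision applies at exactly 10 events, and whether late means after 90 days or after six months. State also whether an event counts when it occurs within 2 years or only as status at the 2-year visit. The choices are the sponsor's.

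Then keep the sample size, the reconciled cut-off and the single-stage test, and add to Study Design:

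- Late grade 3 or higher events within 2 years are tallied as they are confirmed, only in the eligible patients who enter the final test.
- When the rejection number is reached, the primary test is declared and further accrual is put to formal review.

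This costs a sentence or two and a running list, with no change in type I error or power. There are two downsides. If accrual ends early, fewer men remain for the secondary efficacy estimates. The trigger can also fire at a true rate of 10%, which the analysis plan still calls worthwhile: about 15% of trials (11 events) or 25% (10 events) during a 5-year accrual. That is why the trigger should lead to a review and not an automatic stop.

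### The late-toxicity test takes the acceptable rate as its null and advances on non-rejection, and its stated type I error of 0.10 fits only the reversed null

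*Protocol*

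**What the plan says.** Section 8 of the protocol lists toxicity as the primary endpoint, and its Study Design paragraph ties the trial size to it: "Sample size determination is based on the late toxicity endpoint". The size is given as follows: "The target sample size is 100 patients for this Phase II study". The enrolment total then adds an allowance: "Allowing for a 15% ineligibility rate, the total sample size is 115 patients".

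The only formal test is a single-stage Fleming design of the "null hypothesis that the late unacceptable radiation toxicity probability at 2 years p is < 0.05", against an alternative above 0.15, counting grade 3 or higher events. If 10 or fewer patients have such an event, "the null hypothesis will not be rejected and then the regimen will be considered for a phase III study". If at least 10 do, the null is rejected. The paragraph gives the design a power of 89% and a type I error of 0.10.

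**The concern.** The rule decides whether toxicity is low enough to move to phase III. For that kind of question the unacceptable state is normally the null, so that a go means harm has been ruled out at a stated error level. Here the roles are the other way round: the acceptable rate is the null, and the regimen advances because that null survives. Surviving a test is not evidence for the null.

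The labelling also decides what the quoted errors mean. Under the written hypotheses the type I error is the risk of discarding a regimen with 5% toxicity. The risk of more concern to patients, advancing a regimen with 15% toxicity, appears only as one minus the power. A reader who takes 0.10 as the type I error of the written test has the wrong risk in mind. Someone planning phase III would also not learn from the text which toxicity rate a go has excluded.

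**Working it through.** **Inputs**, all from Section 8, Study Design: n = 100; p0 = 0.05; p1 = 0.15; go at 10 or fewer events; stated power 89%; stated type I error 0.10. X is the number of patients with an event, X ~ Binomial(n, p). The text assigns a count of exactly 10 to both decisions, so both readings of the rejection rule are shown.

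**1. The plan's figures under the written hypotheses.** Type I error = P(X ≥ r | p = 0.05) and power = P(X ≥ r | p = 0.15), where r is the lowest count that rejects.

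| Reject at | Type I error | Power |
|---|---|---|
| 11 or more | 0.0115 | 0.9006 |
| 10 or more | 0.0282 | 0.9449 |
| Stated | 0.10 | 0.89 |

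The stated power is close to the first row. The stated type I error matches neither row.

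**2. Where 0.10 fits.** P(X ≤ 10 | p = 0.15) = 1 − 0.9006 = 0.0994. This is the chance of a go at a true 15%. It is the type II error of the test as written, and becomes the type I error only if the null is p ≥ 0.15.

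**3. The reversed test, H0 p ≥ 0.15 versus H1 p ≤ 0.05, go at 10 or fewer.** Type I error = P(X ≤ 10 | p = 0.15) = 0.0994. Power = P(X ≤ 10 | p = 0.05) = 0.9885. So 0.10 agrees with the reversed labelling but 89% does not, while 89% roughly agrees with the written labelling but 0.10 does not. Neither labelling gives both figures. The two stated numbers look like one error and its complement.

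**4. How often the written null survives**, by true rate, at n = 100:

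| True rate | Go at 10 or fewer | Go at 9 or fewer |
|---|---|---|
| 5% | 0.989 | 0.972 |
| 10% | 0.583 | 0.451 |
| 12% | 0.334 | 0.226 |
| 15% | 0.099 | 0.055 |

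A regimen at twice the null rate passes about half the time on either reading.

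**5. What a go at the boundary establishes.** The exact (Clopper-Pearson) one-sided 90% upper bound for x events in n is the 0.90 quantile of Beta(x + 1, n − x).

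| n | Bound at 9 events | Bound at 10 events | Largest count with bound below 15% |
|---|---|---|---|
| 100 | 13.8% | 14.99% | 10 |
| 98 | 14.1% | 15.3% | 9 |
| 97 | 14.3% | 15.4% | 9 |

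At 10/100 the exact two-sided 95% interval is 4.9% to 17.6%. The boundary result therefore excludes 15% at one-sided 90% confidence, but does not show a true rate below 5% or below 10%.

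**6. Why n = 97 or 98 matters.** The plan's own allowance gives 115 × 0.85 = 97.75 evaluable patients, not 100. At 10 events the bound clears 15% by only 0.01 percentage points when n = 100, so losing two or three evaluable patients moves the cut-off to 9.

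**The case against.** The strongest reply is that a two-point rule is defined by its cut-off and its two error probabilities, whichever hypothesis is called the null. With go at 10 or fewer in 100, the chance of advancing a regimen at 15% is already 0.099, and reversing the hypotheses leaves that cut-off unchanged. This stands, and it limits the weight of the point: the rule at n = 100 does not expose patients to an uncontrolled risk at 15%. It does not rescue the stated type I error, which is not that of the stated test.

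A reader might go further and infer that the protocol claims a go demonstrates a rate below 5%. It does not. It says only that the regimen will then be considered for phase III, and the objectives in Section 2.0 speak of evaluating safety and estimating a proportion.

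A reader might also take the sentence in Analysis Plan item 1, "Future studies incorporating DE-SBRT would be worthwhile if the rate of grade 3 GU/GI toxicity was" at most 10%, as a second limit that the test fails to prove. The text does not support this as a separate fault. The sentence concerns grade 3 GU/GI toxicity, mentions neither late onset nor 2 years, and can be read as the cut-off of 10 in 100 expressed as an observed rate.

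Nor does the interval planned for local and distant failure in item 3 show that toxicity will have none. An interval for the primary proportion is commonly left to the SAP, which is not at hand.

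Finally, a go with few events says more than the boundary does. At 5/100 the one-sided 90% upper bound is 9.1%. The limits given above are what the rule guarantees at its edge, not what every go would show.

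**Conclusion.** The point holds as one of labelling, error rates and interpretation. The written test makes acceptable toxicity the null and advances on non-rejection. Its stated type I error of 0.10 is not reproduced on either reading of the cut-off (0.0115 or 0.028). It equals, to rounding, the chance of a go at a true 15% (0.099), which is the type I error of the reversed null. False acceptance at 15% is controlled at about 0.10 in 100 patients, so this should be corrected but does not undermine the decision rule itself.

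The figures assume exact binomial counts, every evaluable patient assessed at 2 years, and exactly 100 evaluable patients except where n = 97 or 98 is shown. The reversed-test figures take 10 events as a go. The mismatch in the type I error does not depend on how a count of 10 is resolved.

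**What to change.** In Section 8, Study Design, restate the test as H0 p ≥ 0.15 versus H1 p ≤ 0.05 for late grade 3 or higher toxicity at 2 years. Define a go as an exact one-sided 90% upper confidence bound below 15%. Give the resulting cut-off by number evaluable: 10 or fewer events at n = 100, and 9 or fewer at n = 97 or 98. Expressing the rule as a bound also assigns every count, including 10, to a single decision.

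For n = 100, replace the stated errors with a type I error of 0.099 (advancing a regimen at 15%) and a power of 0.989 (advancing a regimen at 5%). Add one sentence saying that a go at the boundary excludes 15% at one-sided 90% confidence and does not show a true rate below 5% or 10%.

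This needs rewording only, with no added patients, visits or data. The price is a more modest stated conclusion, and a cut-off of 9 rather than 10 if fewer than 100 patients are evaluable.

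### The go/no-go rule gives opposite decisions at exactly 10 late toxicities, and neither reading of it has the stated 0.10 type I error with 89% power

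*Protocol*

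**What the plan says.** The design is set out in Section 8 of the protocol, under Study Design. The sample size rests on late toxicity: "The target sample size is 100 patients for this Phase II study", with 115 to be enrolled to allow for 15% ineligibility. The test follows a single-stage Fleming design. Its null is worded as "late unacceptable radiation toxicity probability at 2 years p is < 0.05"; its alternative is worded as "toxicity probability at 2 years is > 0.15". The event is toxicity of grade 3 or higher.

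Two adjacent sentences give the decision rule:

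- "If 10 or fewer patients experience late radiation toxicities at 2 years, the null hypothesis will not be rejected", and the regimen is then considered for phase III.
- "If at least 10 patients experience late radiation toxicities at 2 years, the null hypothesis will be rejected".

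The paragraph closes with "This design has a power of 89% and a type I error rate of 0.10". Item 1 of the Analysis Plan in the same section adds a related criterion: "Future studies incorporating DE-SBRT would be worthwhile if the rate of grade 3 GU/GI toxicity was" at most 10%.

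**The concern.** The two decision sentences overlap at a count of 10, where the regimen both goes forward and is rejected. Nothing elsewhere in the protocol resolves this. If 10 events occur, someone will have to choose the reading after seeing the data, which a pre-specified rule is meant to prevent.

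The closing sentence on power and type I error would normally show which reading was meant, but it matches neither. This is the only formal test in the protocol, the only basis for its sample size, and the gate to phase III. A reader therefore cannot tell from the text which rule applies or what error rates it carries.

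**Working it through.** **Inputs**, all from Section 8, Study Design: n = 100; null boundary p0 = 0.05; alternative boundary p1 = 0.15; stated type I error 0.10 and power 89%. X is the number of patients with late toxicity of grade 3 or higher at 2 years, taken as binomial(n, p).

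**Formulas.** For the rule that rejects when X ≥ r:

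- type I error = P(X ≥ r | n, 0.05)
- power = P(X ≥ r | n, 0.15)

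**Step 1: try to reproduce the stated pair at n = 100.**

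| Reject when | Type I error | Power |
|---|---|---|
| X ≥ 8 | 0.128 | 98.8% |
| X ≥ 9 | 0.063 | 97.3% |
| X ≥ 10 (second sentence) | 0.0282 | 94.5% |
| X ≥ 11 (first sentence) | 0.0115 | 90.1% |

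No row gives 0.10 with 89%. The stated type I error is 0.10 / 0.0282 = 3.5 times the attained value under the second sentence and 0.10 / 0.0115 = 8.7 times under the first. The power is 5.5 points off under X ≥ 10 and 1.1 points off under X ≥ 11.

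**Step 2: other routes to the stated pair.**

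- *All 115 enrolled evaluable.* X ≥ 10 gives 0.063 and 98.4%; X ≥ 11 gives 0.029 and 96.7%.
- *Planned accrual less 15%.* 115 × 0.85 = 97.75. With X ≥ 11, n = 98 gives 0.0099 and 88.6%, and n = 99 gives 0.0107 and 89.4%. The power now agrees; the type I error does not.
- *Normal approximation with continuity correction, n = 100.* X ≥ 10 gives 0.019 and 93.8%; X ≥ 11 gives 0.006 and 89.6%.
- *Hypotheses reversed* (null rate 15%, regimen accepted when X ≤ 10, n = 100). Type I error P(X ≤ 10 | 0.15) = 0.099; power P(X ≤ 10 | 0.05) = 98.9%. The 0.10 now agrees; the 89% does not.
- *0.10 read as a ceiling.* The lowest cut-off at n = 100 that keeps type I error at or below 0.10 is X ≥ 9, which neither sentence states.

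A search over n = 20 to 120 finds a close match only at 49 or 50 patients with rejection at 5 or more (n = 50: 0.104 and 88.8%). The protocol mentions no such design, so this does not establish where the figures came from.

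**Step 3: how much the overlap matters at n = 100.**

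| True rate | P(X = 10) | Advance if X ≤ 10 | Advance if X ≤ 9 |
|---|---|---|---|
| 5% | 1.7% | 98.9% | 97.2% |
| 10% | 13.2% | 58.3% | 45.1% |
| 12% | 10.8% | 33.4% | 22.6% |
| 15% | 4.4% | 9.9% | 5.5% |

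At a true rate of 8%, P(X = 10) is 10.2%. The disputed count is thus most likely when the true rate lies between the two hypotheses, where the decision is hardest.

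**The case against.** The strongest defence concerns the power. Under the reading 10 or fewer against 11 or more, 90.1% is close to 89%, and with the 98 or 99 patients implied by the protocol's own ineligibility allowance the power is 88.6% or 89.4%. On that reading only the type I error is wrong, and 0.10 could be a misprint of 0.01 or the type II error put in the wrong place (P(X ≤ 10 | 0.15) = 0.099). This stands: the power figure should not be called wrong under both readings. It also suggests, without proving it, that 11 or more was the intended rejection region.

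Second, the error in the type I rate is harmless in direction. The attained rate is smaller than stated and the power is about as stated or higher, so the sample size is not undermined. That is true, but the sentence still describes a design that is not the one in the paragraph.

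Third, the probability of exactly 10 events is small at the design rates themselves (1.7% at 5%, 4.4% at 15%). That is also true, but a true rate between 5% and 15% is plausible, and there the probability is 10% to 13% at the rates examined from 8% to 12%.

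Fourth, the 10% criterion in the Analysis Plan covers grade 3 gastrointestinal and genitourinary toxicity, while the decision rule counts any toxicity of grade 3 or higher. That criterion therefore cannot settle which reading was meant. None of these points removes the contradiction at 10.

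**Conclusion.** The concern holds. At exactly 10 events the protocol both retains and rejects the null hypothesis. The stated pair of 0.10 and 89% belongs to neither reading: the exact values at n = 100 are 0.028 and 94.5%, or 0.0115 and 90.1%. The clear numerical error is the type I rate; the power is nearly right if rejection starts at 11. Choosing between the readings changes the chance of advancing the regimen by up to about 13 percentage points at the true rates examined.

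These figures assume a binomial count, 100 evaluable patients with 2-year toxicity status known, and the boundary rates 0.05 and 0.15. Using 98, 99 or 115 patients instead does not recover the stated pair. Because this is the only formal decision rule, it must be corrected.

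**What to change.** Rewrite the decision paragraph so that the two regions do not overlap and the error rates belong to the rule. The sponsor should choose one of these, for 100 evaluable patients:

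- null not rejected at 10 or fewer, rejected at 11 or more: exact type I error 0.012, power 90%; or
- null not rejected at 9 or fewer, rejected at 10 or more: exact type I error 0.028, power 94%.

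The first sits more easily with the 10% criterion in the Analysis Plan; if the second is chosen, that criterion should be aligned with it. In either case, say whether the criterion and the rule count the same events.

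It would also help to state that the cut-off will be recomputed by exact binomial if the number evaluable is not 100. A fixed count means different things at different denominators: 11 of 115 is 9.6%, yet it exceeds a limit of 10 events.

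The cost is a wording amendment to one paragraph, with no extra patients. It should be made before the 2-year toxicity counts are known.

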6.0 PATIENT ASSESSMENTS

| Assessment | Pre-entry | | | | Follow-up interval: months post therapy | | | | |
|----------------------------|-----------|---|---|---|---|----|----|-------|---|
| | | 1 | 3 | 6 | 12 | 18 | 24 | 36-60 | |
| History (SHIM, AUA) | X | | X | X | X | X | X | | X |
| Physical exam (DRE) | X | | | X | X | X | X | | X |
| ECOG Performance Scale | X | | | X | X | X | X | | X |
| Prostate Biopsy | X | | | | | | | | |
| PSA | X | | | X | X | X | X | | X |
| Prostate volume assessment | X | | | | | | | | |
| Bone scan | X | | | | | | | | |
| Pelvic imaging | X | | | | | | | | |
| Toxicity evaluation (AUA) | X | | X | X | X | X | X | | X |
| EPIC-26 Questionnaire | X | | | | X | X | | X | X |
| EuroQol EQ-5D-5L | X | | | | X | X | | X | X |

Assessment schedule: Quality of life measurements will take place per the table, then annually through 5 years post-treatment.

7.0 CLINICAL ENDPOINTS:

Patients will have toxicity evaluation weekly during treatment. At 1 month following treatment, patients will be assessed for acute toxicity. At 6, 12, 18, and 24 month intervals (and every year thereafter, through year 5- 10, if investigators opt to continue past year 5), patients will be seen and evaluated, including a history, physical exam, performance status, PSA, toxicity evaluation. In addition, at 6 months, 12 months and annually thereafter, EPIC-26 will be administered. Examination and studies may be done at outside facility. Prostate biopsy, bone scan (PSMA PET/CT may be substituted for bone scan) and pelvic MRI will be performed at time of biochemical or clinical failure.

Criteria for toxicity:

Acute side effects (<=90 days of treatment start) and late side effects (> 90 days of treatment start) will be assessed using the NCI Common Toxicity Criteria version 4.0 (see appendix V).

Criteria for disease control:

1. Biochemical disease free survival (bDFS):
 - a. Phoenix definition (55): failure occurs when the PSA is ≥ 2 ng/ml more than the lowest PSA measurement before the current one, with no backdating. Administration of salvage therapy will be considered failure.

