Quality-Adjusted Life Years (QALY): **EuroQol EQ-5D-5L** is a validated instrument which provides a single index value for a patient’s overall health status (otherwise known as “utility”). It is widely used in cancer clinical trials (56, 57). Five of the items are scored on a 3-point Likert scale (mobility, ability for self-care, ability to perform usual activities, pain/discomfort, anxiety/depression), and one item assesses a patient’s overall health state on a visual analog scale ranging from 0 (worse imaginable state) to 100 (best imaginable).

8. STATISTICAL CONSIDERATIONS:

Endpoints:

Primary Endpoint

1. **Toxicity** will be assessed using the NCI Common Toxicity Criteria version 4.0.

Secondary Endpoints

1. **Biochemical disease-free survival (bDFS)** will be defined as the time in months from completion of SBRT to biochemical failure. Patients who are free from biochemical failure on the date of closing follow-up will be censored on that date. The Phoenix definition will be used to assess biochemical failure as described in Section 10.
2. **Duration of local control** will be defined as the time in months from SBRT completion to local failure.
3. **Distant failure (includes regional failure)** will be defined as the time in months from SBRT completion to distant failure.
4. **Disease-free survival** will be defined as the time in months from the date that the patient is determined to be free of disease to the date of known disease recurrence for any measure of disease. Patients who are alive and free from disease recurrence on the date of closing follow-up will be censored on that date.
5. **Disease-specific survival** will be defined as the time in months from completion of SBRT to death due to prostate cancer, other causes with active malignancy, or complications from treatment. Patients who are alive or dead with disease relapse but with inactive disease on the date of closing will be censored on that date.
6. **Overall survival** will be defined as the time in months from SBRT completion until death. Patients who are alive on the date of closing will be censored on that date.
7. **Quality of life**

Study Design:

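### Local and distant failure are defined as times from SBRT completion but analysed as crude binomial proportions with no time point

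*Protocol*

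**What the plan says.** Section 8 (Secondary Endpoints) gives both endpoints a time origin and a unit. Duration of local control "will be defined as the time in months from SBRT completion to local failure"; distant failure "will be defined as the time in months from SBRT completion to distant failure".

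The analysis does not follow from this. Analysis Plan item 2 covers the other four time endpoints: "Biochemical disease-free survival, disease-free survival, disease-specific and overall survival curves will be calculated and presented by the methods of Kaplan and Meier". Item 3 deals with the remaining two: "The proportion of patients with local and distant failure will be reported with a 95% binomial confidence interval".

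Censoring is treated just as unevenly. For bDFS, Section 8 states: "Patients who are free from biochemical failure on the date of closing follow-up will be censored on that date". Disease-free, disease-specific and overall survival have similar closing-date rules; local control and distant failure have none. Section 7.0 (Criteria for disease control, item 2) does contain a censoring rule for local control: a man who is locally controlled when he has orchiectomy or androgen ablation is censored and is not evaluable for local control from then on.

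On timing, Section 8 says: "Accrual is anticipated to be completed within 5 years of institutional IRB approval". Section 7.0 schedules visits to year 5, and up to year 10 "if investigators opt to continue past year 5". The toxicity endpoint, by contrast, has a fixed time: "the late unacceptable radiation toxicity probability at 2 years".

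**The concern.** A crude proportion estimates the risk of failure by a stated time only if every man is followed to that time and counting stops there. The protocol commits to neither condition. With staggered entry, a man treated late has had less time to fail than one treated early, and item 3 counts both as full members of the denominator. A cut before everyone reaches year 5 understates the 5-year risk. Once everyone has passed year 5, counting later failures overstates it.

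For local control there is a second conflict. A raw proportion cannot censor. A man who has orchiectomy or androgen ablation must either stay in the denominator as a non-failure or be removed, and the protocol does not say which. There is also an ambiguity of wording: Section 5.0 gives every risk group ADT, and Section 7.0 does not say whether that treatment counts as androgen ablation.

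At stake is whether the two rates can be compared with other series or used to plan the phase III studies that Section 8 says this trial should inform. Both endpoints are secondary in Section 8, although Section 2.0 lists them under the primary objective.

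**Working it through.** The protocol states no rate, power or precision for local or distant failure, so there is no figure to reproduce. The calculation shows how far the crude proportion moves with the cut.

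**Inputs from the protocol.** Accrual of up to 5 years; follow-up of 5 years, optionally 10; target n = 100.

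**Assumptions.** Uniform accrual; constant failure hazard; true 5-year risk of 5, 10 or 20%; a cut *c* years after the last patient enters. The earliest plausible final cut is taken as *c* = 2, because toxicity is judged at 2 years.

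**Formula.** λ = −ln(1 − F5)/5. At the cut, potential follow-up *f* is uniform on [*c*, *c* + 5], capped at 5 or 10 years. The expected crude proportion is the average of 1 − exp(−λf).

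**Worked case, F5 = 10%.** λ = −ln(0.9)/5 = 0.02107.
- *c* = 2, capped at 5: the share with at least 5 years is (7 − 5)/5 = 40%. The average failure-free probability is (1/5)(e^(−2λ) − e^(−5λ))/λ + 0.4 × 0.9 = (1/5)(0.9587 − 0.9)/0.02107 + 0.36 = 0.557 + 0.360 = 0.917. The crude proportion is 8.3%.
- *c* = 5, counting to year 10: the average is (1/5)(0.9 − 0.81)/0.02107 = 0.854. The crude proportion is 14.6%.

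**Expected proportion, and coverage of the true 5-year risk by the exact 95% binomial interval (n = 100), no loss:**

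| Cut | True 5% | True 10% | True 20% | Coverage |
|---|---|---|---|---|
| +2 years, capped at 5 | 4.1% | 8.3% | 16.6% | 98 / 92 / 92% |
| +5 years, capped at 5 | 5.0% | 10.0% | 20.0% | 98 / 96 / 97% |
| +5 years, counting to 10 | 7.4% | 14.6% | 28.3% | 88 / 71 / 52% |

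**Adding death and loss.** With 2% per year of each (assumed), the true 5-year cumulative incidence is λ/(λ + μ) × (1 − e^(−5(λ+μ))). With μ = 0.02 this is 0.513 × 0.1857 = 9.5%. Simulation of 4,000 trials of 100 men, mean (SD) in percentage points:

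| Cut | Crude | Aalen-Johansen at 5 years |
|---|---|---|
| +2 years, capped | 7.6 (2.6) | 9.6 (3.5) |
| +5 years, capped | 9.1 (2.9) | 9.6 (3.0) |
| +5 years, counting to 10 | 12.5 (3.3) | 9.5 (3.0) |

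**Section 7 rule.** Same setting, +5 years capped, with 5, 10 or 20% of men having ablation by year 5, independently of failure risk (assumed):
- kept as non-failures: 8.9 / 8.7 / 8.2%
- dropped: 9.3 / 9.5 / 10.0%
- censored, Aalen-Johansen: 9.5 / 9.5 / 9.6%

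**The case against.** The strongest reply is that the practical effect is small. If every man is followed to year 5 and counting stops there, the crude rate is 9.1% against 9.6%, with nearly equal standard errors. On total error the crude proportion is even slightly ahead at two of the three cuts. Root mean squared error, from the unrounded means and SDs against 9.52%, is:
- +2 years, capped: √(1.90² + 2.62²) = 3.2 points crude, 3.5 for Aalen-Johansen
- +5 years, capped: √(0.39² + 2.86²) = 2.9 crude, 3.0 for Aalen-Johansen
- +5 years, counting to 10: √(2.99² + 3.31²) = 4.5 crude, 3.0 for Aalen-Johansen

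This arithmetic is right and limits the seriousness of the point. It does not make the method sound: the crude bias is systematic, and its size and sign depend on a cut date the protocol does not fix.

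The poor coverage figures (88 / 71 / 52%) do require that investigators continue past year 5 and that the result is read as a 5-year rate. That is a fair qualification; with no time point in item 3, nothing prevents it.

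Dropping men labelled not evaluable is one way to read Section 7.0, and it gives 9.3 to 10.0%. But it discards their failure-free time, which is not censoring, and item 3 does not specify it.

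It is also reasonable to read androgen ablation as later treatment, since protocol ADT is meant to start before SBRT. The ambiguity is therefore a minor one to tidy up.

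Finally, a SAP may exist and could supply a time point. The protocol, however, already prescribes a method that does not fit its own endpoint definition, so a SAP would have to depart from it. Kaplan-Meier curves for bDFS and DFS do not fill the gap, because neither separates local from distant failure.

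**Conclusion.** The concern holds. Item 3 fixes an analysis that does not match the two endpoints as Section 8 defines them, names no time, and leaves the Section 7.0 censoring rule without a way to be applied to local control. For distant failure the fault is confined to the missing time point and unequal follow-up.

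For an assumed 10% five-year risk without loss, the expected report ranges from 8.3% to 14.6% across plausible cuts and counting rules; the spread is mainly upward and arises when failures after year 5 are counted. These sizes rest on assumed rates, constant hazard and uniform accrual. The dependence on the cut does not rest on the particular rates chosen. No sample size or decision rule uses either endpoint, so this should be corrected but does not threaten the trial's main conclusion.

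**What to change.** Replace Analysis Plan item 3 with:

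> Cumulative incidence of local failure and of distant failure will be estimated at 5 years from SBRT completion (distant failure also at 2 years) with 95% confidence intervals, with death without failure as a competing event, and censoring at last assessment or, for local failure, at the Section 7 censoring event if earlier.

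Local failure has no 2-year estimate because the histologic criterion in Section 7.0 applies only to biopsies more than 2 years after treatment. Sections 5.0 and 7.0 should also be reconciled so that it is clear whether protocol ADT is a censoring event for local control. This concerns endpoint wording only and changes no treatment.

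The cost is one sentence, one clarified term and a standard routine, with no extra patients or data. Precision is lower at an early cut: at +2 years the standard error rises from 2.6 to 3.5 points while the mean moves from 7.6% to 9.6% (true 9.5%). At +5 years capped the difference is negligible. One limit remains: the estimate assumes that the Section 7 censoring is independent of local failure risk. If ablation follows PSA failure this may not hold, and the change does not cure it.
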